### 5.1 Inclusion Criteria

1.  Subject aged  $\geq$  18 years.
2.  Subjects with non-operable GI cancers requiring multi-modal treatment (e.g. surgery +/- chemo +/-radiation) and have a high likelihood of recurrence and/or treatment failure in the opinion of the treating investigator.
3.  Screen positivity for existential distress on the EDS, defined as scoring  $\geq$  3 on any of the 10 component domains, or a total score  $\geq$  6
4.  ECOG Performance Status  $\leq$  2.
5.  Adequate hepatic function as defined as:
  - Total Bilirubin  $\leq$  1.5x institutional upper limit of normal (ULN) unless elevated bilirubin is related to Gilbert's Syndrome
  - AST(SGOT)/ALT(SGPT)  $\leq$  3  $\times$  institutional ULN
    - Subjects with liver metastases will be allowed to enroll with AST and ALT levels  $\leq$  5  $\times$  ULN.
6.  For subjects of childbearing potential: Negative pregnancy test or evidence of post-menopausal status. The post-menopausal status will be defined as having been amenorrheic for 12 months without an alternative medical cause. The following age-specific requirements apply:
  - Subjects  $<$  50 years of age:
    - Amenorrheic for  $\geq$  12 months following cessation of exogenous hormonal treatments; and
    - Luteinizing hormone and follicle-stimulating hormone levels in the post-menopausal range for the institution; or
    - Underwent surgical sterilization (bilateral oophorectomy or hysterectomy).
  - Subjects  $\geq$  50 years of age:
    - Amenorrheic for 12 months or more following cessation of all exogenous hormonal treatments; or
    - Had radiation-induced menopause with last menses  $>1$  year ago; or

- Had chemotherapy-induced menopause with last menses >1 year ago; or
- Underwent surgical sterilization (bilateral oophorectomy, bilateral salpingectomy, or hysterectomy).

7.  Subjects of childbearing potential and subjects with a sexual partner of childbearing potential must agree to use a highly effective method of contraception as described in Section 5.3.1.

8.  Subjects with a sexual partner of childbearing potential must agree to use a condom during intercourse for 24 hours post- ketamine dose.

9.  Agree to refrain from using any psychoactive drugs, including alcoholic beverages, ondansetron, cannabis, and non-routine PRN medications within 24 hours of each ketamine administration. Exceptions include daily use of caffeine, nicotine, and opioid pain medication (see Section 6.5.1).

10.  Able to provide informed consent and willing to sign an approved consent form that conforms to federal and institutional guidelines.

11.  Agree that for one week preceding the ketamine session, he/she will refrain from taking any nonprescription medication, nutritional supplement, or herbal supplement except when approved by the research team. Exceptions will be evaluated by the research team and will include acetaminophen, non-steroidal anti-inflammatory drugs, and common doses of vitamins and minerals.

12.  Agree not to use nicotine for at least 2 hours before the ketamine administration or for the duration of the ketamine session.

13.  Agree to consume approximately the same amount of caffeine-containing beverage (e.g., coffee, tea) that he/she consumes on a usual morning, before arriving at the research unit on the morning of the ketamine session. If the subject does not routinely consume caffeinated beverages, he or she must agree not to do so on the day of ketamine administration.

14.  Subjects requiring opioid use for pain are on a stable pain management regimen or do not experience clinically significant sedation during opioid use.

- Note: Long-acting opioid medications (e.g., oxycodone sustained-release, morphine sustained release) will be allowed if the last dose occurred at least 6 hours before ketamine administration; such medication will not be taken again until at least 6 hours after ketamine administration.

15.  Fluent in English.

16.  Reading literacy and comprehension sufficient for understanding the consent form and study questionnaires, as evaluated by study staff obtaining consent.

17.  Have a support person who is be able to escort the subject home from the ketamine dosing sessions.

- Note: The use of ride services will not be permitted (e.g., Uber, Lift, taxi, etc.)

## 5.2 Exclusion Criteria

1.  Received ketamine treatments for a psychiatric condition within 6 months of enrollment.
2.  Personal history or first- or second-degree relatives with schizophrenia, bipolar affective disorder, delusional disorder, schizoaffective disorder, psychosis, or other psychotic spectrum illness.
3.  Currently meeting DSM-5 criteria for Dissociative Disorder, or other psychiatric conditions judged to be incompatible with the establishment of rapport or safe exposure to ketamine.
4.  Currently meeting DSM-5 criteria for Cluster B Personality Disorder.
5.  Severe depression requiring immediate standard-of-care treatment (e.g., hospitalization).
6.  Suicidal ideation over the past month as assessed as a yes to question 3, 4, or 5 on the Columbia-Suicide Severity Rating Scale, Suicidal Ideation section
7.  Cancer with known CNS involvement, previously treated brain metastasis, or other major CNS disease.
8.  Current or history within the last two years of meeting DSM-V criteria of substance use disorder (excluding caffeine and nicotine). Current substance use disorders may be identified through the drug urine screening test.
9.  Current evidence of uncontrolled, significant intercurrent illness including, but not limited to, the following conditions:
  - Cardiovascular disorders:
    - Any grade congestive heart failure, unstable angina pectoris, serious cardiac arrhythmias including tachycardia, or clinically significant screening ECG abnormalities.
    - Cardiac hypertrophy or artificial heart valve.
    - Stroke (including transient ischemic attack [TIA]), myocardial infarction (MI), or other ischemic events, or thromboembolic event (eg, deep venous thrombosis, pulmonary embolism), and/or significant coronary artery disease within 3 months before the first dose.
    - QTc prolongation defined as a QTcF > 450 ms.
    - Known congenital long QT.
    - Uncontrolled hypertension defined as  $\geq 140/90$  as assessed from the mean of three consecutive blood pressure measurements taken over 10 minutes.

- Seizure disorder
- Moderate to severe dementia
- History of significant traumatic brain injury
- Requires the use of supplemental oxygen.
- Renal insufficiency as defined as creatinine clearance < 40 mL/min calculated by Cockcroft-Gault formula
- Any other condition that would, in the Investigator's judgment, contraindicate the subject's participation in the clinical study due to safety concerns or compliance with clinical study procedures (e.g., infection/inflammation, intestinal obstruction, unable to swallow medication, [subjects may not receive the drug through a feeding tube], social/ psychological issues, etc.)

10.  Known HIV infection with a detectable viral load within 6 months of the anticipated start of treatment.

Note: Subjects on effective antiretroviral therapy with an undetectable viral load within 6 months of the anticipated start of treatment are eligible for this trial.

11.  Active infection including tuberculosis (clinical evaluation that includes clinical history, physical examination, radiographic findings, and TB testing in line with local practice), hepatitis B (known positive HBV surface antigen (HBsAg) result), or hepatitis C.

Note: Subjects with a past or resolved HBV infection (defined as the presence of hepatitis B core antibody [anti-HBc] and absence of HBsAg) are eligible. Subjects positive for hepatitis C (HCV) antibody are eligible only if polymerase chain reaction is negative for HCV RNA.

12.  Medical, psychiatric, cognitive, or other conditions that may compromise the subject's ability to understand the subject information, give informed consent, comply with the study protocol or complete the study.

13.  Known prior severe hypersensitivity to ketamine or any component in its formulations (NCI CTCAE v5.0 Grade ≥ 3).

14.  Subjects taking prohibited medications as described in Section 6.5.1. A washout period of prohibited medications for a period of at least five half-lives or as clinically indicated should occur before the start of treatment.

## 5.3 Registration

Subjects must complete all screening procedures and meet all of the eligibility requirements before registration. Study-related screening procedures can only begin once the subject has signed the consent form. Subjects must not begin protocol treatment prior to registration.

Treatment should start as soon as logistically possible after registration.

To register eligible subjects on study, complete a Clinical Trials Office Subject Registration Form and submit to [[contact]](mailto:[contact]).

For sites outside of Huntsman Cancer Institute, submit registration forms to [[contact]](mailto:[contact])

### 5.3.1 Contraception

Non-clinical and clinical data describing the effects ketamine on lactation, sperm, and teratogenicity are limited. Therefore, subjects of childbearing potential should have a negative pregnancy test at the time of screening and use a highly effective form of contraception for the duration of study treatment and for at least 14 days after ketamine administration.

Subjects should be instructed to use a condom for 24 hours after the ketamine dose.

Acceptable highly effective contraceptive methods include:

- Bilateral tubal occlusion
- Vasectomized partner
- Intra-uterine devise (IUD) or hormone-releasing system (IUS)
- Any hormonal (estrogen combined with progesterone or progesterone alone) contraception associated with inhibition of ovulation: implanted, oral, intravaginal, transdermal, or injectable.
- Spermicide with a compatible barrier method (i.e. diaphragm, sponge, or male or female condoms).
- Abstinence from heterosexual intercourse.

## 5.4 Screen Failures

Screen failures are defined as participants who consent to participate in the clinical trial but do not meet subject eligibility criteria. These subjects will not be entered into the study or begin study intervention. However, minimal information is required to ensure transparent reporting of screen failure participants to meet the Consolidated Standards of Reporting Trials (CONSORT) publishing requirements. Minimal information includes, but may not be limited to, demography, screen failure details, eligibility criteria, and any serious adverse event (SAE) experienced during screening, but prior to being deemed ineligible. Adverse events and SAEs will not be collected after a subject is deemed ineligible. Any AEs/SAEs related to a screening procedure will be followed until resolution.

Individuals who do not meet the criteria for participation in this trial (screen failure) may be rescreened at the Investigator's discretion.

## 5.5 Strategies for Recruitment

Potential patients will be identified by Investigators in the setting of their outpatient clinics. Social work team members on each oncology service will help identify potential patients during routine clinic encounters.

### 5.5.1 Number of Subjects

The study will enroll 12 subjects.

### 5.5.2 Number of Study Sites

This will be a single-center trial run at the Huntsman Cancer Institute at the University of Utah.

## 6 STUDY INTERVENTION

### 6.1 Ketamine Assisted Psychotherapy

Ketamine-assisted psychotherapy will be administered standard of care by the therapist team in the HMHI Park City Ketamine-Assisted Psychotherapy Clinic. This team has been trained specifically in this modality of treatment by the Psychedelic Research and Training Institute (PRATI). This modality of therapy involves an initial experiential phase following ketamine administration of approximately 1 hour that is supportive and non-directive in nature and may utilize eye-shades and music playlists via headphones. Interventions during this phase of the session are minimal, supportive, and largely directed towards helping the patient move through any difficult emotions or experiences arising. The next phase of the 3 hour session involves more directed psychotherapeutic engagement where participants begin to explore and discuss content that arose during their experience, how this content may be related to underlying issues that bring them into this study (existential distress, grief, depressive symptoms, anxiety), and strategies to integrate this material or insights gained into their everyday lives. Modalities employed by our therapist team largely center around Acceptance and Commitment Therapy (ACT) techniques however also include – as clinically indicated- other modalities such as CBT, psychodynamic approaches, and Internal Family Systems (IFS), and Internal Family Systems (IFS).

### 6.2 Ketamine Administration Schedule

Ketamine and all other supportive medications described in this guideline will be stored in accordance with State and Federal regulations. Medication retrieval, documentation, and wasting will follow applicable organizational policies and guidelines related to automated dispensing cabinets, controlled substances, and the storage, labeling, and discarding of drugs. Each vial of ketamine will be used to provide the desired dose for a single patient, and the remainder of the vial will be promptly wasted.

#### 6.2.1 Personnel required for administration of ketamine:

- Medical doctor will be in the same room as the patient or onsite and immediately available throughout ketamine administration and the monitoring period

- Vital signs will be performed by either a medical assistant, clinic therapist, nurse, or medical doctor. All vital signs will be reviewed by an MD during the session at the time they are taken.

#### **6.2.2 Screening prior to ketamine-assisted psychotherapy:**

- Evaluation and screening **prior to first visit**
  - Psychiatric evaluation and review of medical history
  - Physical exam
- Evaluation and screening **immediately prior to each administration**
  - Confirm allergy list
  - Confirm patient has been NPO (except for water) for at least 4 hours prior to treatment
  - Medication history
    - Confirm no use of sedatives or psychostimulants for 12 hours prior to treatment
    - Confirm no use of MAO inhibitors for 2 weeks prior to treatment
  - Brief physical assessment
    - Blood pressure
      - If blood pressure > 140/90 mmHg, then make a clinical decision regarding risks/benefits of administration of ketamine
      - If blood pressure > 160/100 then hold ketamine and re-check after five minutes. May repeat this process twice.
      - If blood pressure remains over 160/100 then ketamine will not be given.
    - Other parameters that must be met for ketamine administration
      - Oxygen saturation > 92% on room air
      - Respirations > 8 breaths per minute
      - Patient must be fully awake
      - Patient must be able to move all extremities
  - Verify the patient has a responsible adult to escort them home
    - Patients may take any mode of transportation as long as they are accompanied by an escort
    - Ketamine will not be administered if an escort cannot be identified

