## 1.2 Schema

#### 1.4 Schedule of Events

Activity	Screening	Preparatory Session (Baseline)	Ketamine Sessions 			Integration Session	Follow-Up 		
			1	2	3		14 Days	30 Days	90 Days
Visit						0	(±3)	(±7)	(±7)
(Window in days)	-60	0							
Informed Consent	X								
Demographics	X								
Medical History	X								
Eligibility Criteria	X								
Registration 	X								
Clinical and Laboratory Assessments									
Vital Signs 	X		X 	X 	X 				
Physical Exam	X								
ECOG Score	X								
ECG	X		ACI						
Adverse event collection 	X	X	X	X	X	X	X		
Concomitant medications	X	X	X	X	X	X	X		
Complete Metabolic Panel	X								
Urine Drug Screen	X								
Pregnancy Test 	X								
Study Intervention									
Evaluation and Screening 			X	X	X				

Activity	Screening	Preparatory Session (Baseline)	Ketamine Sessions 			Integration Session	Follow-Up 		
			1	2	3		14 Days	30 Days	90 Days
Visit						0	(±3)	(±7)	(±7)
(Window in days)	-60	0							
Ketamine Administration 			X	X	X				
Psychotherapy		X	X	X	X	X			
Assessments									
EDS 	X	X	X	X	X		X	X	X
QIDS-SR-16 		X	X	X	X		X	X	X
C-SSRS Baseline/Screening 	X								
C-SSRS Since Last Visit 		X	X	X	X	X	X		
MEQ-30 			X	X	X				
NADA 			X	X	X				
DADDS 		X	X	X	X		X	X	X
FACIT-Sp 		X					X	X	X
Storyline Integrative Assessment 		X					X	X	X

---

 Ketamine will be given during three sessions, 2 to 7 days apart. Questionnaires, with the exception of the MEQ, may be completed up to 1 day prior to the ketamine session.

 Follow-up will be based on time since completion of the integration session.

 To register eligible patients on study, complete a Clinical Trials Office Subject Registration Form and submit to [[contact]](mailto:[contact]).

 Laboratory assessments should be completed within 28 days of enrollment.

 Vital signs include systolic/diastolic blood pressure, heart rate, respiration rate, pulse oximetry and weight.

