Ketamine is stored at the HMHI KAP Clinic and administered by an MD study investigator. The HMHI KAP Clinic employs a log of ketamine administration in accordance with DEA standards. Appropriate records will be kept to accurately show all dispensing activities including the return of any unused Investigational Product (IP). IP will be supplied only to subjects deemed eligible for study therapy. IP may not be dispensed to patients who have not been enrolled in the trial.

Patients will be advised to refrain from the following for 24 hours before ketamine:

- Cannabis
- Alcoholic beverages
- Psychoactive drugs
- Non-routine PRN medications
- Grapefruit, grapefruit juice, and other CYP4A inhibitors

On the day of ketamine administration, patients on opioids should not take any long-acting opioids within 6 hours prior to or 6 hours proceeding ketamine administration. Patients should consume approximately the same amount of caffeine-containing beverage (e.g., coffee, tea) that he/she consumes on a usual morning, before arriving at the research unit. If the subject does not routinely consume caffeinated beverages, he or she must agree not to do so on the day of ketamine administration. Patients should also not use nicotine for at least 2 hours before ketamine administration.

All doses of ketamine will be administered at the investigational site by qualified medical staff. The time of administration will be recorded in the patients' research charts. Any reason for deviation from the protocol-specified dose or schedule will be documented in the subject's research chart.

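### The usual-morning-caffeine instruction gives no interval to dosing and can make a compliant patient fail the 4-hour fasting check; separately, two transport rules disagree

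*Combined protocol and SAP*

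**What the plan says.** **Fasting.** Section 6.2.2 lists checks to be made "immediately prior to each administration". One of them reads: "Confirm patient has been NPO (except for water) for at least 4 hours prior to treatment". Water is the only exemption.

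**Caffeine.** Inclusion criterion 13 (Section 5.1) has habitual users agree to drink about the amount of coffee or tea "that he/she consumes on a usual morning, before arriving at the research unit on the morning of the ketamine session". The dosing-day text at the end of Section 6.2.4 repeats the instruction, "Patients should consume approximately the same amount of caffeine-containing beverage", and Section 6.6.1 carries the same sentence. People who do not routinely drink caffeine must abstain on the dosing day, so the instruction to drink concerns habitual users only.

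**Neighbouring rules.** Inclusion criterion 9 restricts psychoactive drugs within 24 hours of dosing and then adds: "Exceptions include daily use of caffeine, nicotine, and opioid pain medication". Inclusion criterion 12, on nicotine, does set an interval to dosing: "Agree not to use nicotine for at least 2 hours before the ketamine administration".

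**Transport.** The note to inclusion criterion 17 rules out ride services and names taxis among them. Section 6.2.2 accepts any form of transport provided an escort goes with the patient.

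**The concern.** The fast is a safety check made just before a drug that Section 3.1 describes as a dissociative anesthetic. Section 6.2.4 plans for vomiting, obtundation and bag ventilation after the injection, which is the setting in which a fast protects the patient. Yet the caffeine instruction lets a habitual user drink coffee right up to arrival. That person has done what the protocol asked and may still be unfasted when staff make the check. Dosing is then either delayed or given without the fast that Section 6.2.2 asks for.

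Section 6.2.2 does not say which. It states that ketamine is not given if blood pressure stays above 160/100 or if no escort can be identified, but it attaches no action to a failed fast.

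The transport mismatch is smaller. Patients and staff can get different answers on whether an escorted taxi home is acceptable, depending on which section they read.

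**Working it through.** The plan states no figure on this point, so there is nothing to reproduce. The check is a comparison of the rules, followed by one line of arithmetic.

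**Step 1: can both caffeine rules be met?** Yes, but only if the drink is finished at least 4 hours before the injection. A later drink satisfies inclusion criterion 13 and Sections 6.2.4 and 6.6.1 and fails the check in Section 6.2.2. The three caffeine texts fix only the latest time, which is arrival. None of them mentions the fast or gives an interval to dosing.

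**Step 2: does another rule reconcile them?** The caffeine exception in inclusion criterion 9 is an exception to the 24-hour psychoactive-drug rule and does not mention the fast. The nicotine rule shows that the protocol can state an interval to dosing when it intends one. No other text addresses the overlap.

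**Step 3: how many doses could be involved?** Section 5.5.1: "The study will enroll 12 subjects". Schedule of Events, footnote 1: "Ketamine will be given during three sessions, 2 to 7 days apart". The ceiling is therefore 12 × 3 = 36 planned doses. It would be reached only if every participant were a habitual user, and the documents do not give that share.

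**Step 4: how early must the drink end?** Let *w* be the wait in hours from arrival to injection. The documents do not give *w*, so the values below are assumptions. The smallest gap between finishing the drink and arriving that passes the check is

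gap = max(0, 4 − *w*).

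| Assumed wait *w* (h) | 4 − *w* | Drink must end at least this long before arrival (h) |
|---|---|---|
| 0.5 | 4 − 0.5 | 3.5 |
| 1 | 4 − 1 | 3 |
| 2 | 4 − 2 | 2 |
| 4 | 4 − 4 | 0 |

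A drink taken just before arriving passes only if the wait is 4 hours or more.

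**Step 5: transport.** Take a patient going home by taxi with a responsible adult. The note to inclusion criterion 17 forbids it and Section 6.2.2 permits it. No timing assumption is needed, and no frequency can be given.

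**The case against.** The strongest reply is that the caffeine rules lack an interval but do not contradict each other. A drink finished 4 or more hours before dosing satisfies every sentence, and the pre-dose check should find an unfasted patient before the injection. Dosing without the fast would mean that staff disregarded the check, which is a deviation under Section 10.5 and not something the plan instructs. The likelier result is a delayed or rescheduled session. The frequency is unknown, and 36 is simply every planned dose.

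Much of this stands. The rules can be met together, the check is a real safeguard, and the table in the working shows the timing constraint without showing that any patient would fail. What remains is that the instruction reaches the patient before arrival and the check comes afterwards, when the coffee has already been drunk. Skipping the drink is not clearly compliant either: inclusion criterion 13 is an agreement to consume the usual amount, and Section 5 requires eligibility to hold up to dosing.

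On transport, both texts require an escort, Section 6.2.2 withholds ketamine without one, and Section 6.2.4 requires an adult escort for at least 3 hours afterwards. Protection against an impaired patient travelling alone is therefore the same under either text. The bar in inclusion criterion 17 might also be read as the controlling rule, since eligibility must persist to dosing. That limits the consequence, but the literal conflict over an escorted taxi remains.

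**Conclusion.** Both points hold on the current text, and both should be corrected. Following the caffeine instruction as written can produce a failed fasting check before an anesthetic drug, and the protocol names no action for that failure. This affects habitual users only, at no more than 36 planned doses. The actual number depends on session times, the wait from arrival to dosing and the share of habitual users, none of which is given. Confidence is high in the comparison of the texts and does not extend to how often the conflict would arise.

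The transport conflict is direct but minor, because an escort is required either way. The two points are independent and neither adds weight to the other. No effect is claimed on the completion endpoint, the sample size or the analysis.

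**What to change.** Keep the 4-hour fast. In inclusion criterion 13 and the dosing-day text of Sections 6.2.4 and 6.6.1, state that usual caffeine is to be finished at least 4 hours before dosing, or skipped if that is not possible. This takes the same form as the existing 2-hour nicotine rule, and amending criterion 13 itself makes skipping compliant. Exempting black coffee or tea from the fast would also remove the conflict, but it would loosen a safety check.

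Use one transport rule in both inclusion criterion 17 and Section 6.2.2. One option is to allow ride services only when the responsible adult escort is present. That relaxes the present bar, so if the sponsor wants to keep the bar, copy it into Section 6.2.2 instead.

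The cost is wording in an amendment and in the patient instructions. The practical downside is that some habitual users will drink very early, go without caffeine, or be dosed later in the day.
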